5.6 Potential Benefits

Potential benefits of a NULOJIX® (belatacept) regimen include avoidance of long term side effects associated with the prolonged use of CNI, such as nephrotoxicity, hypertension, dyslipidemia, and glucose intolerance, and avoidance of sirolimus-related toxicity such as buccal ulcers and dyslipidemia.

Tacrolimus is known to be directly beta-cell toxic in vitro and in vivo, and has been associated with new onset immunosuppression-related diabetes in non-diabetic recipients of solid organ transplants.

Overall, the administration of thymoglobulin to adult renal transplant patients has been safe and effective. Prolonged depletion of T cells has been achieved but has not been accompanied by increased incidence of opportunistic infection or other serious complications. This treatment has generally led to substantial overall reduction in chronic immunosuppression but not tolerance.

6 SELECTION OF PARTICIPANTS

6.1 Selection of Centers

The centers conducting this study have significant experience in SPK transplantation.

Additional centers may be recruited if enrollment is lower than anticipated. The team will evaluate enrollment progress 6 and 12 months after initiation of the study. If enrollment is not satisfactory, we will expand the number of centers involved to accommodate additional participants.

6.2 Inclusion Criteria

Patients who meet all of the following criteria are eligible for enrollment as study participants:

- 1. Male or Female, 18-55 years of age at the time of enrollment;
- 2. Ability to understand and provide written informed consent;
- 3. Candidate for a primary simultaneous kidney and pancreas allograft with random c-peptide <0.3 ng/mL.
- 4. No known contraindications to study therapy using NULOJIX® (belatacept);
- 5. Female subjects of childbearing potential must have a negative pregnancy test upon study entry;
- 6. Female and male participants with reproductive potential must agree to use FDA approved methods of birth control during participation in the study and for 4 months following study completion;
- 7. No donor specific antibodies prior to transplant that are considered to be of clinical significance by the site investigator;
- 8. Negative crossmatch, actual or virtual, or a PRA of 0% on historic and admission sera, as determined by each participating study center.
- 9. A documented negative TB test within the 12 months prior to transplant. If documentation is not present at the time of transplantation, and the subject does not have any risk factors for TB, a TB-specific interferon gamma release assay (IGRA) may be performed.

6.3 Exclusion Criteria

Patients who meet *any* of these criteria are *not* eligible for enrollment as study participants:

- 1. Need for multi-organ transplantation other than a kidney and pancreas
- 2. Recipient of previous organ transplant;
- 3. Active infection including hepatitis B, hepatitis C, or HIV;
- 4. Individuals who have required treatment with systemic prednisone or other immunosuppressive drugs within 1 year prior to transplant;
- 5. Individuals previously treated with NULOJIX® (belatacept);
- 6. Any condition that, in the opinion of the investigator, would interfere with the participant's ability to comply with study requirements;
- 7. Use of investigational drugs within 4 weeks of enrollment;
- 8. Known hypersensitivity to mycophenolate mofetil (MMF)or any of the drug's components;
- 9. Administration of live attenuated vaccine(s) within 8 weeks of enrollment.
- 10. EBV sero-negative recipients or recipients whose EBV status is unknown or ambiguous prior to the time of transplantation

Viral Capsid Antigen IgG	Viral Capsid Antigen IgM	EBV Nuclear Antigen	Interpretation	Belatacept
Positive	Negative	Positive	Past Infection (EBV positive)	Eligible
Positive	Positive	Positive	Likely resolved EBV (EBV positive)	Eligible
Positive	Negative	Negative	Recent EBV vs. EBNA negative past infection (EBV positive)	Eligible
Negative	Negative	Negative	Naïve (EBV negative)	Ineligible
Negative	Negative	Positive	Possibly a false positive	Ineligible ¹
Positive	Positive	Negative	Recent infection	Ineligible ²

[figure not shown]
1. If on subsequent testing the IgG and/or IgM turn positive the subject is eligible.

2. The subject will be deemed eligible if on subsequent testing the EBNA turns positive or if EBV-PCR testing is negative.

7 STUDY DESIGN

This trial is a prospective, multi-center, open-label, phase II, randomized (1:1) study to compare a NULOJIX® (belatacept) based immunosuppressive regimen to a CNI-based regimen in recipients of SPK. Subjects will be consented and enrolled until a total of 60 subjects are randomized.

Clinical Trials in Organ Transplantation (CTOT) CONFIDENTIAL Protocol CTOT-15

8 STUDY THERAPY REGIMEN

The study therapy regimen includes:

Control Arm

- ◆ Induction: 5 day course of MEDROL® (methylprednisolone) or equivalent;
- Induction: Thymoglobulin® (Anti-thymocyte Globulin (Rabbit));
- Maintenance Immunosuppression: Prograf® (tacrolimus), or generic;
- Maintenance Immunosuppression: CellCept® (mycophenolate mofetil- MMF), or Myfortic® (mycophenolate sodium), or generic.

Investigational Arm

- ◆ Induction: 5 day course of MEDROL[®] (methylprednisolone) or equivalent;
- Induction: Thymoglobulin® (Anti-thymocyte Globulin (Rabbit));
- Maintenance Immunosuppression: NULOJIX® (belatacept);
- Maintenance Immunosuppression: Prograf® (tacrolimus), or generic;
- Maintenance Immunosuppression: CellCept® (mycophenolate mofetil- MMF), or Myfortic® (mycophenolate sodium), or generic.

[figure not shown]

Figure 2. CTOT-15 Study Therapy Regimen

Study T	herapy Dosage	
CATEGORY	DRUG	DOSING
Investigational Agent	NULOJIX ® (belatacept)	INVESTIGATIONAL ARM: Participants will receive NULOJIX [®] (belatacept) 10mg/kg on days 5, 14, 28, 56 and 84. After 84 days, subjects will receive belatacept at the maintenance dose of 5 mg/kg every 4 weeks until completion of the trial.
Induction Therapy	Medrol [®] methylprednisolone	BOTH STUDY GROUPS : Methylprednisolone will be administered at a target dose of 500 mg beginning on the day of transplant, and tapered to 250 mg day 1 post-transplant, 125 mg day 2 post-transplant, 60 mg day 3 post-transplant, and 30 mg day 4 post-transplant. IV methylprednisolone will be administered over no less than 30 minutes in accordance with the applicable product labeling.
Induction Therapy	Thymoglobulin® (Anti-thymocyte Globulin (Rabbit))	BOTH STUDY GROUPS: The Thymoglobulin® target dosage is 6mg/kg total over 3 to 4 days. The recommended route of administration is intravenous infusion using a high-flow vein. Thymoglobulin should be infused over a minimum of 6 hours for the first infusion and over at least 4 hours on subsequent days of therapy. The infusion will be monitored per the center practice/SOPs. Premedication with corticosteroids, acetaminophen, and/or an antihistamine 1 hour prior to the infusion will be given per center practice and may reduce the incidence and intensity of side effects during the infusion. Medical personnel should monitor patients for adverse events during and after infusion.
Maintenance Immunosuppression	Mycophenolate Acid	BOTH STUDY GROUPS : CellCept [®] (Mycophenolate Mofetil- MMF) will be administered at a target dose of 1000 mg PO or IV BID beginning on the day of surgery or post- operative day 1 depending upon when during the day the surgery is completed (maximum MMF dosing is 2G per day). MMF will be adjusted based on clinical complications (such as neutropenia). Myfortic [®] (mycophenolate sodium) may be used as a replacement for MMF. Mycophenolate sodium will be dosed at 720 mg PO or IV BID. Mycophenolate sodium will be adjusted based on clinical complications.
Maintenance Immunosuppression	Prograf® (tacrolimus)	Tacrolimus may be discontinued or target levels adjusted at the discretion of the Investigator. CONTROL ARM: The site investigator will identify a starting tacrolimus dose at their discretion in order to achieve the target trough levels no later than 5 days post-transplantation. Tacrolimus dosing will be initiated on the day of surgery or post-operative day 1 depending upon when during the day the surgery is completed, then adjusted to target trough levels of 8-12 ng/ml during the first 24 weeks post-transplant, then adjusted to target trough levels of 5-8 ng/ml thereafter. INVESTIGATIONAL ARM: The site investigator will identify a starting tacrolimus dose at their discretion, in order to achieve the target trough levels no later than 5 days post-transplantation. Tacrolimus dosing will be initiated on the day of surgery or post-operative day 1 depending upon when during the day the surgery is completed. The dosage will be adjusted to achieve the following therapeutic trough levels: 5-8 ng/ml during the first 24 weeks post-transplant and then 3-5 ng/ml until day 280 (week 40). Subjects may be withdrawn if they meet all the criteria defined below. Tacrolimus Withdrawal: Subjects participating in the Investigational Arm will be considered eligible for withdraw of tacrolimus once they have reached the week 40 study visit, if all of the following is met:
		 No evidence of cellular or antibody mediated rejection in the first 280 days post- transplant. Stable renal allograft function as measured by serum creatinine over the preceding 90 days.

Protocol CTOT-15					 
	3. Stable pancreatic fund serum amylase/lipase			ng blood sugars, HbA1c, a	and
	4. The absence of donor		-	ransplant.	
	If eligible for withdrawal, t period. The chart below sh tacrolimus dose.	•			nd
	Start of withdrawal tacrolimus dose	Initial dose reduction	dose	4 weeks later	
			reduction		
	0.5 mg q12h (Prograf level < 5 ng/ml)	0.5 mg daily	Discontinue		
	0.5mg q12h (Prograf level > 5 ng/ml)	0.5 mg daily	0.5mg every other day	Discontinue	
	1mg daily (Prograf level < 5 ng/ml)	0.5 mg daily	Discontinue		
	1mg daily (Prograf level > 5 ng/ml)	0.5 mg daily	0.5mg every other day	Discontinue	
	1mg q12h (Prograf level < 5 ng/ml)	1 mg daily	Discontinue		
	1mg q12h (Prograf level > 5 ng/ml)	0.5 mg q12h	0.5 mg daily	Discontinue	
	2mg q12h (Prograf level < 5 ng/ml)	1 mg q12	1 mg daily	Discontinue	
	2mg q12h (Prograf level > 5 ng/ml)	1.5 mg q12h	1 mg q12h	Discontinue	
	3 mg q12h	2 mg q12h	1 mg q12h	Discontinue	
	4 mg q12h	3 mg q12h	2 mg q12h	Discontinue	
	5 mg q12h	3 mg q12h	2 mg q12h	Discontinue	
	6 mg q12h	4 mg q12h	2 mg q12h	Discontinue	
	7 mg q12h	5 mg q12h	3 mg q12h	Discontinue	
	8 mg q12h	6 mg q12h	3 mg q12h	Discontinue	
	9 mg q12h	6 mg q12h	3 mg q12h	Discontinue	
	10 mg q12h	7 mg q12h	4 mg q12h	Discontinue	
	Monitoring during Program weaning period and for 6 weaning period and for 6 weaning period and for 6 weat and the set of	weeks following tor for early sign , amylase, and lip not able to return nvestigator and o subject will not scretion of the si (tacrolimus)- S	complete withdrav is of rejection. This base. Labs may be n to the study cent clinical decisions m continue with tacr ite investigator. ubjects participatir	val, weekly safety labs wil includes a serum performed by the subject' er. All results should be ade accordingly. If any sig olimus withdrawal and ng in the Investigational A	t's gns Arm

any of the following events occur: 1 - An acute rejection episode 2- Request of the subject or site Investigator.

8.1 Investigational Drug: NULOJIX® (belatacept)

Nulojix® (belatacept), a selective T-cell costimulation blocker, is a soluble fusion protein consisting of the modified extracellular domain of CTLA-4 fused to a portion (hinge-CH2-CH3 domains) of the Fc domain of a human immunoglobulin G1 antibody. Belatacept is produced by recombinant DNA technology in a mammalian cell expression system. Two amino acid substitutions (L104 to E; A29 to Y) were made in the ligand binding region of CTLA-4. As a result of these modifications, belatacept binds CD80 and CD86 more avidly than abatacept, the parent CTLA4-Immunoglobulin (CTLA4-Ig) molecule from which it is derived. The molecular weight of belatacept is approximately 90 kilodaltons.

NULOJIX® (belatacept), along with 1 non-siliconized single-use syringes (Norm-Ject®), will be supplied by Bristol-Myers Squibb (Princeton, NJ). Please refer to section 5.1, and to applicable product labeling for known and potential risks to human participants associated with the study medication(s).

NULOJIX® (belatacept) is indicated for prophylaxis of organ rejection in adult patients receiving a kidney transplant. NULOJIX® (belatacept) is to be used in combination with basiliximab induction, mycophenolate mofetil, and corticosteroids. NULOJIX® (belatacept) should only be used in subjects who are EBV seropositive. Use of NULOJIX® (belatacept) for the prophylaxis of organ rejection in transplanted organs other than kidney has not been established. The current study will investigate the ability of NULOJIX® (belatacept) to facilitate a maintenance regiment that avoids both CNI and corticosteroids following SPK transplantation.

8.1.1 Formulation, Packaging, and Labeling

NULOJIX® (belatacept) is supplied as a sterile, white or off-white lyophilized powder for intravenous administration. Prior to use, the lyophile is reconstituted with a suitable fluid to obtain a clear to slightly opalescent, colorless to pale yellow solution, with a pH in the range of 7.2 to 7.8. Suitable fluids for constitution of the lyophile include SWFI, 0.9% NS, or D5W. Each 250 mg single-use vial of Nulojix also contains: monobasic sodium phosphate (34.5 mg), sodium chloride (5.8 mg), and sucrose (500 mg).

NULOJIX® (NDC 0003-0371-13) will be provided as open-label commercially available supplies. NULOJIX® is packaged in cases of 6 individually boxed vials and syringes. Each case contains the NDC number, lot number, expiration date, product identity and strength, the number of vials, route of administration, and storage requirements. The study label will be affixed to each case and will include the IND number, the protocol number, the Sponsor, the Manufacturer, and the statement "New Drug- Investigational Use Only".

8.1.2 Preparation, Administration, and Dosage

NULOJIX® is for intravenous infusion only. Subjects do not require premedication prior to administration of NULOJIX®. The total infusion dose of NULOJIX® should be based on the actual body weight of the patient at the time of transplantation, and should not be modified during the course of therapy, unless there is a change in body weight of greater than 10%.

The prescribed dose of NULOJIX ®must be evenly divisible by 12.5 mg in order for the dose to be prepared accurately using the reconstituted solution and the *silicone-free disposable syringe* provided. Evenly divisible increments are 0, 12.5, 25, 37.5, 50, 62.5, 75, 87.5, and 100. For example:

A patient weighs 64 kg. The dose is 10 mg per kg.

- Calculated Dose: 64 kg × 10 mg per kg = 640 mg
- The closest doses evenly divisible by 12.5 mg below and above 640 mg are 637.5 mg and 650 mg.
- The nearest dose to 640 mg is 637.5 mg.
- Therefore, the actual prescribed dose for the patient should be 637.5 mg.

INVESTIGATIONAL ARM ONLY: Participants will receive NULOJIX® (belatacept) 10mg/kg through a peripheral vein on days 5, 14, 28, 56 and 84 After 84 days, subjects will receive NULOJIX® (belatacept) at the maintenance dose of 5 mg/kg every 4 weeks until completion of the trial.

Preparation for Administration

- 1) Calculate the number of Nulojix vials required to provide the total infusion dose. Each vial contains 250 mg of belatacept lyophilized powder.
- 2) Reconstitute the contents of each vial of Nulojix with 10.5 mL of a suitable diluent using the silicone-free disposable syringe provided with each vial and an 18- to 21-gauge needle. Suitable diluents include: sterile water for injection (SWFI), 0.9% sodium chloride (NS), or 5% dextrose in water (D5W).

Note: If the Nulojix powder is accidentally reconstituted using a different syringe than the one provided, the solution may develop a few translucent particles. Discard any solutions prepared using siliconized syringes.

- 3) To reconstitute the Nulojix powder, remove the flip-top from the vial and wipe the top with an alcohol swab. Insert the syringe needle into the vial through the center of the rubber stopper and direct the stream of diluent (10.5 mL of SWFI, NS, or D5W) to the glass wall of the vial.
- 4) To minimize foam formation, rotate the vial and invert with gentle swirling until the contents are completely dissolved. Avoid prolonged or vigorous agitation. Do not shake.
- 5) The reconstituted solution contains a belatacept concentration of 25 mg/mL and should be clear to slightly opalescent and colorless to pale yellow. Do not use if opaque particles, discoloration, or other foreign particles are present.
- 6) Calculate the total volume of the reconstituted 25 mg/mL Nulojix solution required to provide the total infusion dose.

Volume of 25 mg/mL Nulojix solution (in mL) = Prescribed Dose (in mg) ÷ 25 mg/mL

- 7) Prior to intravenous infusion, the required volume of the reconstituted Nulojix solution must be further diluted with a suitable infusion fluid (NS or D5W). Nulojix should be reconstituted with:
 - SWFI should be further diluted with either NS or D5W
 - NS should be further diluted with NS
 - D5W should be further diluted with D5W
- 8) From the appropriate size infusion container, withdraw a volume of infusion fluid that is equal to the volume of the reconstituted Nulojix solution required to provide the prescribed dose. With the same silicone-free disposable syringe used for reconstitution, withdraw the required amount of

belatacept solution from the vial, inject it into the infusion container, and gently rotate the infusion container to ensure mixing.

The final belatacept concentration in the infusion container should range from 2 mg/mL to 10 mg/mL. Typically, an infusion volume of 100 mL will be appropriate for most patients and doses, but total infusion volumes ranging from 50 mL to 250 mL may be used. Any unused solution remaining in the vials must be discarded.

- 9) Prior to administration, the Nulojix infusion should be inspected visually for particulate matter and discoloration. Discard the infusion if any particulate matter or discoloration is observed.
- 10) The entire Nulojix infusion should be administered over a period of 30 minutes and must be administered with an infusion set and a sterile, non-pyrogenic, low-protein-binding filter (with a pore size of $0.2-1.2 \ \mu$ m).
 - The reconstituted solution should be transferred from the vial to the infusion bag or bottle immediately. The Nulojix infusion must be completed within 24 hours of reconstitution of the Nulojix lyophilized powder. If not used immediately, the infusion solution may be stored under refrigeration conditions: 2°-8°C (36°-46°F) and protected from light for up to 24 hours (a maximum of 4 hours of the total 24 hours can be at room temperature: 20°-25°C [68°-77°F] and room light).
 - Infuse Nulojix in a separate line from other concomitantly infused agents. Nulojix should not be infused concomitantly in the same intravenous line with other agents. No physical or biochemical compatibility studies have been conducted to evaluate the co administration of Nulojix with other agents.

8.1.3 Handling, Dispensing, and Destruction of NULOJIX® (belatacept)

Care should be taken when handling the injectable drug products. Proper aseptic techniques should be used when preparing and administering sterile products such as belatacept. Gloves are recommended during constitution process. If belatacept concentrate or solution comes in contact with skin or mucosa, immediately and thoroughly wash with soap and water.

NULOJIX® (belatacept) vials are single-use vials and do not contain preservatives. Therefore after reconstitution, the vials should be used immediately whenever possible. The belatacept 250 mg vial should be stored under refrigeration (2-8°C), and should be protected from long term exposure to light. Intact vials are stable for at least 1 year under these conditions.

Reconstituted solutions of belatacept at a concentration of 25 mg/mL are stable for 24 hours in the vials if stored at room temperature (15-25°C) and ambient lighting conditions, or under refrigeration. When further diluted with 5% Dextrose for Injection or 0.9% Normal Saline Solution to a belatacept concentration as low as 2 mg/mL, solutions may be stored in plastic, non-siliconized IV bags for up to 24 hours at room temperature and ambient lighting conditions or under refrigeration. The belatacept infusion must be completed within 24 hours of constitution of the lyophilized powder. Storage of reconstituted solutions in syringes is not recommended due to stability and potential bacterial contamination.

Belatacept should be stored in a secure area according to local regulations. It is the responsibility of the Investigator to ensure that belatacept is only dispensed to study participants. Belatacept must be dispensed only from official study sites by authorized personnel according to local regulations. The

Investigator should ensure that belatacept is stored in accordance with the environmental conditions (temperature, light and humidity) as determined by the Sponsor and defined in the Investigator Brochure or SmPC/reference label.

If an investigational product is destroyed at the site, it is the investigator's responsibility to ensure that arrangements have been made for the disposal, procedures for proper disposal have been established according to applicable regulations and guidelines and institutional procedures, and appropriate records of the disposal have been documented. The unused investigational products can only be destroyed after being inspected and reconciled by the responsible study monitor.

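### Sections 8.1.2 and 8.1.3 set incompatible room-temperature and light limits for diluted belatacept (at most 4 hours v up to 24 hours) and must be reconciled

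*Combined protocol and SAP*

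**What the plan says.** Section 8.1.2 (Preparation, Administration, and Dosage), step 10, deals with the solution after it has been diluted in the infusion container. "If not used immediately, the infusion solution may be stored under refrigeration conditions", at 2-8°C and protected from light, for up to 24 hours. Within that period "a maximum of 4 hours of the total 24 hours can be at room temperature", which the step defines as 20-25°C and room light.

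Section 8.1.3 (Handling, Dispensing, and Destruction) deals with solution diluted in 5% dextrose or 0.9% saline and held in infusion bags. It says that such "solutions may be stored in plastic, non-siliconized IV bags for up to 24 hours at room temperature and ambient lighting conditions or under refrigeration".

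The sections agree on the overall limit. Section 8.1.2: "The Nulojix infusion must be completed within 24 hours of reconstitution of the Nulojix lyophilized powder". Section 8.1.3: "The belatacept infusion must be completed within 24 hours of constitution of the lyophilized powder".

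Section 8.1.3 also makes the investigator responsible for storing the drug under conditions "as determined by the Sponsor and defined in the Investigator Brochure or SmPC/reference label". The content of those sources is not reproduced in the protocol.

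**The concern.** Both statements are current body text, both concern the same product in the same state, and neither is said to take precedence. A pharmacist with a diluted bag that has stood at room temperature for six hours finds it outside the limit in one section and inside it in the other. A monitor could not say from the protocol alone whether giving that bag was a deviation.

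The discard instructions do not settle the matter. The one for a prepared infusion rests on visual inspection: "Discard the infusion if any particulate matter or discoloration is observed". The others, in section 8.1.2, cover solution made up with siliconized syringes and solution left over in the vials. None refers to time at a given temperature.

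The product contains no preservative (section 8.1.3), so the storage time of a prepared infusion could bear on patient safety. The risk is possible; the documents do not demonstrate it.

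**Working it through.** No statistical quantity is involved. The check is a comparison of the two sections.

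| Condition for diluted solution in the infusion container | Section 8.1.2, step 10 | Section 8.1.3 |
|---|---|---|
| Refrigerated | Up to 24 h at 2-8°C | Up to 24 h |
| Room temperature | At most 4 h of the 24 h | Up to 24 h |
| Light | Protected, except during the room-temperature allowance | Ambient light allowed throughout room-temperature storage |
| Infusion completed | Within 24 h of reconstitution | Within 24 h of reconstitution |

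**Same product state?** Yes. In section 8.1.2 the dilution takes place in steps 7 and 8, so the infusion solution in step 10 is the diluted product. Section 8.1.3 gives the 25 mg/mL solution in vials a sentence of its own, then repeats the 24-hour room-temperature allowance for the diluted solution in bags. A distinction between vial and bag therefore does not explain the difference.

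**Size of the gap.** The room-temperature limits differ by 24 − 4 = 20 hours, a ratio of 24/4 = 6.

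**Where the sections clash**, by time at room temperature:

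- 4 hours or less: allowed by both.
- More than 4 and up to 24 hours: allowed by 8.1.3, not by 8.1.2.
- Beyond 24 hours: allowed by neither.

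The infusion itself takes 30 minutes (step 10) and must fit within the same 24 hours, so storage can last at most 24 − 0.5 = 23.5 hours. That trims the top of the middle band and leaves the conflict as it is.

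**Light.** Section 8.1.2 allows room light only within its 4-hour allowance. Section 8.1.3 allows ambient light for the whole room-temperature period. The two therefore clash over the same band.

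**A smaller mismatch.** Section 8.1.2 defines room temperature as 20-25°C. The only range in section 8.1.3 is 15-25°C, in its sentence on vials. One definition should serve both.

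**The case against.** The strongest case on the other side is that the practical effect is narrow.

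- **Shared limit.** Both sections set the same 24-hour completion limit, and a bag stored within the terms of 8.1.2 meets 8.1.3 as well. This stands, and it confines the conflict to the middle band.
- **Outside reference.** Section 8.1.3 names the Investigator Brochure or label, and the commercial cases carry storage requirements (section 8.1.1). Sites may therefore have an answer elsewhere. This stands in part: the protocol does not say that those sources override either sentence, and their content is not available here.
- **Late stage of the trial.** Version 7.0 is dated June 28, 2016. Its amendment moves the experimental arm to physician-directed treatment, with study belatacept available until August 31, 2016. That is 2 + 31 + 31 = 64 days, and 64/28 ≈ 2.3, so about two or three four-weekly infusions remain for those who stay on the drug. This also stands and limits the remaining exposure.

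A reader might be tempted by three stronger claims that the documents do not support.

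- **That the sections also contradict each other on vials.** Section 8.1.2 says that the reconstituted solution "should be transferred from the vial to the infusion bag or bottle immediately", while 8.1.3 describes 24-hour stability in the vial. But 8.1.3 also asks for reconstituted vials to be used at once where possible. Its 24-hour figure states stability and does not tell sites to hold the vial.
- **That every infusion is affected.** Appendix 2 schedules 5 infusions on days 5 to 84 and 10 at weeks 16 to 52, so 5 + 10 = 15 by week 52. That counts scheduled infusions. Only bags kept more than 4 hours at room temperature fall in the conflict.
- **That dosing becomes inconsistent across sites.** Storage time does not change the prescribed dose, and the documents give no evidence of lost potency in bags between 4 and 24 hours. The contamination remark in 8.1.3 concerns syringes.

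**Conclusion.** The point holds as an internal inconsistency in the drug-handling text: two storage limits for diluted belatacept, differing by 20 hours at room temperature and in protection from light, with nothing in the protocol to say which prevails. It affects only bags kept at room temperature for more than 4 and up to 24 hours. How many bags that is cannot be estimated from the documents.

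It would go too far to infer that sites cannot tell which infusions to discard: outside that band the two sections give the same answer. The conflict is wrong as written and has a possible bearing on patient safety, but the correction is minor. The primary endpoint, power and analysis are unaffected.

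The conclusion assumes that both sections describe the same diluted product, which the order of the preparation steps supports, and that no document outside this set has been declared to override either sentence.

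**What to change.** The sponsor and pharmacy should reconcile section 8.1.2, step 10, with section 8.1.3 against the Investigator Brochure or label that 8.1.3 names. The protocol should then state one storage-time limit, one light-protection requirement and one definition of room temperature for the diluted solution, in one place, with the other section referring to it. It should also say which source governs if the protocol and the label differ. Site pharmacies should be notified. This review does not say which limit is right.

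The cost is a wording correction and a pharmacy notice. No change to the design, sample size or analysis is needed.
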